5.0 MEASUREMENT OF EFFECT

5.1 ENDPOINTS

Objectives: The endpoints are detection of residual tumor and of normal tissue. The *primary* endpoint will be correspondence between intensity of *in vivo* fluorescence and PpIX concentration and the pathologist's quantification of tumor in biopsy specimens, e.g. percent tumor present. The measures used in the *secondary* objective will be PpIX concentration, $\mu\text{g}/\text{mg}$ and intra-operative fluorescence intensity. Measures used in the *third objective* will be the biopsy specimen's fluorescence intensity and the MR image enhancement at the biopsy site's intraoperative stereotactic coordinates as determined by the surgeon.

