8.0 STATISTICAL CONSIDERATIONS

8.1 STATISTICAL ANALYSIS PLAN

Primary objective: We will assess 2 doses of 5-ALA, 10mg/kg and 20mg/kg, to determine the optimum ALA dose in terms of both sensitivity and specificity for residual tumor. The endpoint will be correspondence between intensity of *in vivo* fluorescence and PpIX concentration and the pathologist's quantification of tumor in biopsy specimens, e.g. percent tumor present. Receiver operating characteristic (ROC) curves will be calculated for each of the 2 combinations of ALA dose to estimate a level of fluorescence that distinguishes residual tumor from normal tissue with large true positive fraction (TPF) and small false positive fraction (FPF). A joint 95% confidence region for TPF FPF will be calculated, using $\alpha^*=1-\sqrt{1-\alpha}=0.975$ and univariate confidence limits for the individual probabilities. Having chosen the cut-points for each of the 4 combinations, positive and negative predictive values and diagnostic likelihood ratios will be calculated to describe the characteristics of each [18].

To compare the test characteristics of each ALA dose and to assess how the test characteristics are affected by demographic, disease, and surgical characteristics we will

fit multivariable generalized mixed models to tumor and normal biopsy specimens using robust standard errors to account for the correlation of samples taken from the same individual.

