Secondary Objective: We will assess the correlation between the recorded *in vivo* qualitative assessment of fluorescence signal from the neurosurgeon with the post-surgical (i.e., *ex vivo*) absolute PpIX concentration detected in *ex vivo* tissue biopsies. The surgeon will subjectively score the intra-operatively observed fluorescence level as follows: 0, no fluorescence, 1, low fluorescence, 2, moderate fluorescence, or 3, high fluorescence [after 16]. We will first graph fluorescence against each PpIX concentration measurement (intraoperative and *ex vivo*) to evaluate the shape of the relationship. Additionally we will calculate a Spearman's correlation coefficient with 95% confidence interval to assess the correlation between fluorescence against each PpIX concentration measurement (intraoperative and *ex vivo*). The sensitivity and specificity of these observations will be determined [after 16], where the sensitivity of observable intraoperative PpIX fluorescence is the probability of observable intraoperative fluorescence given the presence of tumor cells in the tissue and specificity is the probability of no observable intraoperative fluorescence given that there are no tumor cells in the tissue [16]. We will also explore whether dose, patient, and disease characteristics affect the strength of the relationship between these measurements using multivariable generalized mixed models.

Tertiary Objective: To determine the association between the presence of fluorescence in the surgical cavity and the post-operative image enhancement on MRI. This includes the relationship between the amount and location of residual tumor detected by fluorescence, PpIX concentration, and intra-operative frameless stereotaxy following maximal resection versus the amount and location of tumor imaged post-operatively via CT and/or MRI. Assessment of agreement between fluorescence, intra-operative PpIX concentration, and MR intensity will be explored using the radiologist's assessment of MR intensity, measured on an ordinal scale. A multivariable ordinal logistic model will be fitted to assess the strength of the relationship and whether dose, patient or disease characteristics affect the relationship.

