8.2 SAMPLE SIZE AND STATISTICAL POWER

Our study is powered appropriately for determination of the primary objective which involves the assessment of 2 doses of 5-ALA, 10mg/kg and 20mg/kg, to determine the optimum ALA dose in terms of both sensitivity and specificity for residual tumor. We calculate the total sample size for 80% power at the 0.05 significance level, given that the sensitivity will decrease by 15% with decreasing ALA dose within patient group (i.e. newly diagnosed or recurrent). Therefore our null hypothesis is that the sensitivity of the 10mg/kg dose is less than or equal to 15% different from the 20 mg/kg dose and the

alternative hypothesis is that the sensitivity of the 10mg/kg dose is greater than 15% different from the 20 mg/kg dose. We also take into account having multiple biopsies per individual on study. The total sample size per group per dose is as follows:

The primary objective of this Phase II study is to estimate and compare the combined diagnostic accuracy of in-vivo qualitative assessment of fluorescent signal in detecting residual tumor when used by the neurosurgeon using 2 doses of 5-ALA: 10 mg/kg and 20 mg/kg. The in-vivo qualitative assessment by the neurosurgeon will be coded on an ordinal scale ranging from 0 (no signal) to 3 (highest signal), as was done in a similar study reported by Roberts et al (J Neurosurg 2010 Apr 9, epub ahead of print) using a dose of 20 mg/kg in newly diagnosed gliomas. As in Roberts et al, we assume a score of 1 or higher will be considered positive. In the study by Roberts et al (2010) the reported sensitivity and specificity were 0.75 and 0.71, respectively, using the histopathologic reading as gold standard. In this study, because having high sensitivity and specificity are both important in terms of avoiding false negatives (which would involve not removing residual tissue) and false positives (removing normal tissue), the Youden index, defined as Sensitivity + Specificity -1 will be used as an overall measure of diagnostic accuracy. This study is designed so that if the dose levels of 10 and 20 mg/kg have true Youden indices that differ by 0.10 or more, then the probability is 80% or higher that the observed Youden index will be higher for the group with the higher actual index, i.e., the probability of selecting the correct dose level based on observed Youden indices will be 80% or higher.

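### Section 8.2 claims 80% power at the 0.05 level for a 15% sensitivity difference, but n=30 supports only a Youden selection rule, which 5.1 and 8.1 do not carry as the primary analysis

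*Combined protocol and SAP*

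**What the plan says.** The combined protocol and SAP describes the primary comparison in three ways.

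- **Correspondence.** Section 5.1 says the primary "endpoint will be correspondence between intensity of *in vivo* fluorescence and PpIX concentration" with the pathologist's quantification of tumor, for which percent tumor is given as an example. Section 8.1 repeats this and plans the analysis: "Receiver operating characteristic (ROC) curves will be calculated for each of the 2 combinations of ALA dose to estimate a level of fluorescence" that separates tumor from normal tissue. After the cut-points are chosen, "positive and negative predictive values and diagnostic likelihood ratios will be calculated to describe the characteristics of each". To compare doses, the plan is to "fit multivariable generalized mixed models to tumor and normal biopsy specimens" with robust standard errors.
- **Sensitivity hypothesis.** The first paragraph of 8.2 claims 80% power at the 0.05 level, "given that the sensitivity will decrease by 15% with decreasing ALA dose within patient group". Its null is a difference of 15% or less and its alternative is a difference above 15%. Sidedness is not stated.
- **Youden selection.** The second paragraph of 8.2 restates the primary objective as the accuracy of the surgeon's 0 to 3 score, counts a score of 1 or higher as positive, and says "the Youden index, defined as Sensitivity + Specificity -1 will be used as an overall measure of diagnostic accuracy". The design target is at least 80% probability that the truly better dose shows the higher observed index when the indices differ by 0.10.

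In 8.1 the surgeon's score appears under the secondary objective, where "The sensitivity and specificity of these observations will be determined". The Youden index and the selection rule appear only in 8.2.

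**The concern.** The trial exists to determine the optimum dose (Section 2.2). If the stated power belongs to one quantity, the sample size to a second and the primary endpoint to a third, the 80% figure can be attached to a result that it does not cover. The power claim in the first paragraph of 8.2 is a specific statement that can be tested against n=30. The other two descriptions differ in instrument (intensity and PpIX against the surgeon's score), in cut-point (chosen from the data against fixed) and in decision (none stated against selection of the higher index). That leaves open which result decides the dose.

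**Working it through.** **Inputs, all from 8.2.** n=30 per dose per stratum; 3 tumor-positive and 3 tumor-negative samples per patient; ρ=0.1 or 0.2; variance of each proportion p(1−p)(1+2ρ)/(3n); sensitivity 0.75 at 20 mg/kg; Youden difference 0.10.

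**Step 1: reproduce the sample-size table.** Let V be the sum of p(1−p) over the two sensitivities and two specificities. The probability of correct selection is Φ(0.10/SE) with SE = √[V(1+2ρ)/(3n)], so

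n = z(0.80)² × V × (1+2ρ) / (3 × 0.10²).

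- Row 1 (0.75, 0.70 against 0.60, 0.75): 23.4 and 27.3; stated 23 and 27.
- Row 5 (0.65, 0.70 against 0.55, 0.70): V = 0.2275+0.21+0.2475+0.21 = 0.895, giving 25.4 and 29.6; stated 25 and 30.

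All 24 entries agree to within one patient. The formula has no alpha term. At n=30 the correct-selection probability over the 12 rows is 0.820 to 0.844 (ρ=0.1) and 0.802 to 0.825 (ρ=0.2). The arithmetic for the selection rule is sound.

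**Step 2: the 15% sensitivity claim at n=30.** Assume an absolute drop of 15 points (0.75 to 0.60) and a null of zero difference. Then 0.75×0.25 + 0.60×0.40 = 0.4275, with 3×30 = 90 tumor samples per dose.

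| | ρ=0.1 | ρ=0.2 |
|---|---|---|
| SE = √[0.4275(1+2ρ)/90] | 0.0755 | 0.0815 |
| 0.15/SE | 1.987 | 1.839 |
| Two-sided power, Φ(0.15/SE − 1.96) | 0.51 | 0.45 |
| One-sided power, Φ(0.15/SE − 1.645) | 0.63 | 0.58 |

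For 80% two-sided power, (1.96+0.8416)² × 0.4275 × (1+2ρ)/(3×0.15²) gives 60 (ρ=0.1) or 70 (ρ=0.2) patients per dose per stratum. A pooled-variance formula gives 61 or 71.

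**Step 3: the null as written.** With a null of a difference of 15% or less, a true 15% difference sits on the null boundary. Any valid test rejects there with probability of about alpha, whatever the sample size, so 80% power at that difference is not attainable.

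**Step 4: the Youden comparison as a significance test.** Two-sided power for a 0.10 difference is Φ(0.10/SE − 1.96). Over the table rows at n=30 it is 0.15 to 0.17 (ρ=0.1) and 0.13 to 0.15 (ρ=0.2). Reaching 80% would take 231 to 281 or 270 to 328 patients per dose per stratum. So n=30 supports selection and not a test.

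**Step 5: the correspondence endpoint.** The documents give no sample size or precision for it.

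**The case against.** Five points can be made for the plan.

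1. **The Youden index can be obtained from 8.1.** A reader might infer that 8.1 lacks the fixed cut and that an analyst following it could never produce the deciding statistic. The documents do not support that. The secondary objective in 8.1 defines sensitivity and specificity by observable against no observable fluorescence on the 0 to 3 score, which is a cut of 1 or higher. Section 8.1 also estimates true and false positive fractions, and 8.2 says that the index will be used. The fault is placement and a missing decision rule. What remains is that the index from the ROC analysis would use a data-chosen cut, so it is not the one that was sized.
2. **Section 5.1 is not only about percent tumor.** It opens by naming detection of residual tumor and of normal tissue as the endpoints, and percent tumor is an example. The descriptions are therefore related, but this does not say which one decides the dose.
3. **The power figures test a null of zero, which 8.2 does not state.** This is correct, and they are labelled as resting on that assumption. The null actually written fares worse (Step 3). Reading 15% as relative would mean a smaller drop (0.75×0.85 = 0.6375) and lower power.
4. **Pooling strata would come close to the claim.** With 60 per dose, 0.15/√[0.4275(1+2ρ)/180] is 2.810 or 2.601, so two-sided power is 0.80 (ρ=0.1) or 0.74 (ρ=0.2). But 8.2 places the hypothesis within patient group, and its table is per group.
5. **Making every quantitative analysis secondary would conflict with 2.2**, which asks for comparison by both qualitative and quantitative imaging. This stands, and the fix respects it.

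**Conclusion.** The concern holds in this form: 8.2 states a power that the design does not have for the hypothesis it names, and the quantity that sizes the trial is not the one that 5.1 and 8.1 make primary. Stated power is 80%. At n=30 within a stratum it is about 0.51 or 0.45 two-sided and 0.63 or 0.58 one-sided, assuming an absolute 15-point drop from 0.75, a null of zero difference, 3 tumor samples per patient and ρ of 0.1 or 0.2. Under the literal null it is about alpha.

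A reader might go on to infer that the sample size is miscalculated or that the trial is too small for its purpose. That does not follow: n=30 delivers the 80% that 8.2 claims for selecting on observed Youden indices.

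**What to change.** 1. In 8.2, delete the 15% sensitivity hypothesis with its 80% power and 0.05 level, or restate the power that n=30 delivers and correct the null.
2. In 5.1 and 8.1, state that the dose decision rests, within each stratum, on the observed Youden index of the surgeon's score at 1 or higher, using the selection rule already in 8.2. Report the difference between doses with a patient-clustered confidence interval, and describe the procedure as selection, not as a significance test. From the SEs in Step 1, the expected 95% half-width is about 1.96×0.099 = 0.19 to 1.96×0.118 = 0.23, so the interval will usually include zero when the true difference is 0.10.
3. Keep the ROC and PpIX analyses that the quantitative part of 2.2 requires, label them as estimation not covered by the 80% figure, and align 2.2, 5.1, 8.1 and 8.2.

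Sample size and planned measurements do not change. The 0 to 3 score should be added to the data list in 6.1, which names only the surgeon's tumor/normal classification, although 4.4.2 (Surgical Treatment) and 8.1 imply that the score is recorded. The cost is an amendment to protocol and SAP wording, and a less favourable statement of power.

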5.2 DATA ANALYSIS

5.2.1 FLUORESCENCE INTENSITY LEVELS VS. HISTOPATHOLOGY

The data sets will be collated into the 4 study groups (2 ALA doses and 2 study arms-- i.e., newly diagnosed and recurrent diagnosis) for analysis purposes.

Histopathology of the 1st part of the biopsies, performed by a single experienced neuropathologist (**i.e., [name]**) will be used as the gold standard. The white-light, fluorescence images, and intra-operative PpIX concentration readings will be compared to assess the sensitivity and specificity for biopsy-confirmed visible tumor.

5.2.2 Intra-operative vs. *Ex Vivo* PpIX EXTRACTION ASSAY

The intra-operatively determined PpIX concentration will be compared to the intra-operative imaging, ex vivo PpIX concentration, and MR enhancement images. This analysis will facilitate an assessment of the utility of lower ALA doses for enhancing subjective and/or quantitative contrast of tumor versus background fluorescence and/or PpIX concentration.

5.2.3 CONFOCAL FLUORESCENCE MICROSCOPY VS. HISTOPATHOLOGY

The confocal fluorescence microscopy images and adjacent H&E sections will be compared to determine the relationship between microscopic localization of PpIX fluorescence, concentration, and tumor cells.

6.0 STATISTICAL PARAMETERS

6.1 PATIENT DATA SET

For each patient the following data will be captured for analysis (collection timing in parens):

1. Patient demographic information (at enrollment).
2. Tumor/normal tissue classification for each biopsy by the neurosurgeon (intra-operatively).
3. Histology report on 1st part of biopsies (one to several weeks post-operatively).
4. PpIX extraction assay 2nd part of biopsies (one to several months post-operatively).
5. Confocal microscopy fluorescence images on 3rd part of biopsies (one to several months post-operatively).
6. White light images of biopsy sites (i.e. of the tissue area around the biopsy location; intra-operatively).
7. Fluorescence images of biopsy sites over an area sufficient to clearly demarcate the region of interest (intra-operatively).
8. PpIX concentration at biopsy site.
9. Frameless stereotaxy coordinates of biopsies (intra-operatively).
10. Magnetic Resonance appearance of biopsy at coordinates taken in #8 (one to several weeks post-operatively).
11. Magnetic Resonance image volumes (i.e., pre-, intra-, and post-operative; one to several weeks post-operatively).

7.0 DRUG FORMULATION AND PROCUREMENT

7.1 ALA FORMULATION AND TOXICITIES

7.1.1 ALA Formula

The chemical formula for ALA is:

Three common synonyms also used to refer to ALA are:

δ -Aminolevulinic acid Hydrochloride

5-Amino-4-oxopentanoic acid Hydrochloride

5-Aminolaevulinic acid Hydrochloride

7.1.2 ALA PREPARATION

ALA (5-amino levulinic acid) is provided in powder form. Patients receive ALA orally, dissolved in orange juice or sterile water (< 60 ml) [14,15,19-40]. ALA is stored in powder form by the investigational pharmacist. Before use the ALA is weighed by the pharmacist and the surgeon or his delegate. The ALA is then dissolved in orange juice or sterile water maximally 15 min prior to ingestion by the patient.

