4.2 RANDOMIZATION

Patients who have consented to this protocol will be randomly assigned to one of two ALA dose groups (Table 3). Randomization will be stratified by whether the tumor is newly diagnosed (i.e. *de novo*) or recurrent. The data center will prepare sealed, opaque envelopes with the randomized assignment to ALA dose and administration time and notify the pharmacy of the trial site so that so that the correct ALA dose can be prepared.

Neurosurgeons and investigators responsible for determining pathologic characteristics, for quantifying fluorescence images, for extracting chemical PpIX, for co-localizing fluorescence images with MR images will be blinded to the ALA dose and administration time. In case of emergency, such as toxicity or allergic reaction attributable to the drug, the research pharmacist on call will break the blind and inform the PI and the physician responsible for clinical management.

A safety monitoring board has been developed at the Case Comprehensive Cancer Center at Case Western Reserve University. Also, forms will be filled out by the surgeon postoperatively on a daily basis, the patient's surgeon will report any adverse effects. In addition to specific signs and symptoms, liver function tests will be ascertained at 48

hours and, if abnormal, these tests will be continued on a twice-weekly basis until they peak and then at weekly intervals thereafter to resolution. In the case of any adverse event, the patient will be examined by the study physician and appropriate medical action taken.

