4.4.2 LIGHT SENSITIVITY PRECAUTIONS

Before ALA administration, patients will be given verbal and written instructions for protection from sunlight by the staff surgeon or his delegate (see Section 4.7.1). It should be noted that these patients are hospitalized following surgery, so that there is in practice a very small possibility of their being exposed to bright sunlight outdoors. Nursing staff in the recovery room and on the ward will be instructed regarding the need to avoid accidental exposure to bright light in the first 24 hours.

4.4.3 .PATIENT GROUPS AND NUMBERS AND ALA DOSE

This clinical trial has ALA dose at 2 levels (10 and 20 mg/kg) and ALA administration time at 1 time point (3h). Consenting patients scheduled for surgery will be assigned to primary or recurrent arm based on clinical presentation, are then randomly assigned to one of two groups (for dose assignment) within each of the two arms of the study. Sample sizes of the 4 patient groups with two ALA dose levels are listed in the table below:

Table 3: Study Design and Sample Size

	Administration Time	
	3 hours New D _x	3 hours Recurrent D _x
10 mg/kg	30	30
20 mg/kg	30	30

For both patients with new and recurrent disease, biopsies will be taken at up to six sites identified by the surgeon: in the tumor center, tumor edge, area surrounding the tumor (if safe), areas seen to fluoresce intraoperatively and an area with MR enhancement outside

the tumor region (if this can be accomplished safely). Prior to collecting these biopsies readings will be taken at the biopsied location with the PpIX point probe by the surgeon. For each of the 6 biopsies, they will be divided into 3 parts and distributed for further analysis as follows: one portion will be sent to the pathologist for assessment of tumor percentage, one portion will be evaluated by the Division of Biophysics at the University of Toronto for PpIX concentration and the other for assessment of fluorescence.

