7.3 ALA STORAGE

ALA is provided in powder form in 10 g vials.

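### Neurosurgeons are to be blinded to ALA dose (4.2), yet 7.1.2 lets the surgeon, or a delegate with no stated independence, weigh it, so the person who scores fluorescence could infer the arm

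*Combined protocol and SAP*

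**What the plan says.** **The blind.** Section 4.2 lists who is blinded, starting with "Neurosurgeons and investigators responsible for determining pathologic characteristics" and going on to those who quantify images, extract PpIX and match images to MR. All of them "will be blinded to the ALA dose and administration time". The only route to unblinding it gives is the on-call research pharmacist, in an emergency.

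**The weighing.** Section 7.1.2: "Before use the ALA is weighed by the pharmacist and the surgeon or his delegate". Section 7.3: "ALA is provided in powder form in 10 g vials". The drug is therefore not supplied as patient-sized doses, and each dose has to be weighed out. Sections 4.1 and 4.4.3 (Patient Groups and Numbers and ALA Dose) set the two arms at 10 and 20 mg/kg.

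**The score.** Section 8.1, under the secondary objective: "The surgeon will subjectively score the intra-operatively observed fluorescence level", on a scale from 0 to 3. Section 8.2 makes the neurosurgeon's qualitative assessment the basis of the dose comparison and dichotomizes it: "we assume a score of 1 or higher will be considered positive". The same section states a prior expectation: "given that the sensitivity will decrease by 15% with decreasing ALA dose within patient group".

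**The concern.** Under 7.1.2 the person who scores fluorescence is a permitted weigher of a dose that 4.2 conceals from that person. The two sections can both be followed only if a delegate always weighs and keeps the mass from the surgeon, and neither condition is stated.

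The outcome most exposed is a subjective reading in which the line between 0 and 1 decides positive or negative. A surgeon who has inferred the arm also has, from Section 8.2, an expectation about how the lower dose will perform. The blind in 4.2 is there to keep that expectation out of the score.

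Biopsy-site choice is a lesser route. Sections 4.4.2 (Surgical Treatment) and 4.4.3 (Patient Groups and Numbers and ALA Dose) leave it to the surgeon, but 4.4.3.1 has tumor and normal sites identified under white light and 8.2 fixes the site categories. Point-probe readings are instrument values, and histology is read by a separate, blinded pathologist; neither is claimed as a route of bias here.

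**Working it through.** **1. The texts side by side**

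| Question | 4.2 | 7.1.2 |
|---|---|---|
| May the neurosurgeon know the dose? | No | Yes in effect, by weighing it |
| Who handles dose information? | Data center and pharmacy | Pharmacist plus surgeon or delegate |
| Must the delegate be independent? | Not addressed | Not stated |
| Is the mass kept from the surgeon? | Implied by the blind | Not stated |

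The sealed envelopes in 4.2 conceal the allocation; they do not hide the mass on the balance. Section 4.4.2 (Light Sensitivity Precautions) gives the patient's instructions "for protection from sunlight by the staff surgeon or his delegate", so a surgeon's delegate also appears there, again with no stated independence.

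**2. Does the mass reveal the arm?** Mass = body weight × dose. With assumed body weights:

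- 50 kg: 500 or 1,000 mg
- 70 kg: 700 or 1,400 mg
- 100 kg: 1,000 or 2,000 mg

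For a given patient the ratio is always two, so mass together with body weight gives the arm.

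**3. The plan's own sizing.** Inputs from Section 8.2: 3 tumor-positive and 3 tumor-negative samples per patient, n = 30 per dose and stratum, variance of each estimated sensitivity or specificity p(1−p)(1+2ρ)/(3n), ρ = 0.1 or 0.2, and a true Youden difference of 0.10. With S the sum of p(1−p) over the two sensitivities and two specificities:

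- Required n = S × (1+2ρ)/3 × (0.8416/0.10)²
- SD of the Youden difference = √[S × (1+2ρ)/(3n)]
- P(correct selection) = Φ(0.10/SD)

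Table 1 in 8.2, row 0.65/0.70 versus 0.55/0.70: S = 0.2275 + 0.2100 + 0.2475 + 0.2100 = 0.895. At ρ = 0.2, required n = 0.895 × 1.4/3 × 70.83 = 29.6, which rounds up to 30, the plan's figure. All 24 entries of the table reproduce to within one patient.

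**4. Margin at n = 30.** In the same row SD = √(0.895 × 1.4/90) = 0.118 and P = Φ(0.10/0.118) = 0.802. The net Youden shift toward the worse dose at which P equals 0.80 is 0.10 − 0.8416 × SD. Each dose cell has 3 × 30 = 90 samples of each tissue status, so a shift confined to one status in one cell equals shift × 90 calls. Over the 12 rows:

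| | ρ = 0.2 | ρ = 0.1 |
|---|---|---|
| SD | 0.107-0.118 | 0.099-0.109 |
| P, no shift | 0.802-0.825 | 0.820-0.844 |
| Shift bringing P to 0.80 | 0.0007-0.0100 | 0.0081-0.0167 |
| Same, in calls of 90 | 0.06-0.90 | 0.73-1.50 |

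**5. Illustration, with assumed shifts.** P = Φ((0.10 − shift)/SD) at ρ = 0.2:

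- Shift 0.03 (2.7 of 90 calls): 0.723-0.744
- Shift 0.05 (4.5 of 90 calls): 0.664-0.680

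These are net averages over a cell. Patients whose dose the surgeon did not weigh dilute them, and a shift in the other direction raises P.

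**The case against.** **An ambiguity, not a breach.** Section 4.2 is the specific rule on blinding, 7.1.2 offers a delegate, and the weighing surgeon is not said to be the scoring surgeon. This is right as far as it goes: nothing shows that the blind will be broken. But the surgeon remains a permitted weigher, and nothing separates the two roles.

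**The thin margin is not specific to this defect.** Any design sized to about 80% has little slack at its design alternative. That stands. The figures show what the design can absorb, not how large the bias is.

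**A threshold shift partly cancels.** A surgeon who scores the lower dose more sparingly would lower sensitivity and raise specificity. Moving 3 of 90 tumor calls and 3 of 90 normal calls from positive to negative changes the Youden index by −3/90 + 3/90 = 0. This stands too: the counts above are net, and the gross number of altered calls could be much larger.

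**Pooling the strata.** If the doses were compared over both strata, with n = 60 per dose and ρ = 0.2, the same formulas give P = 0.885-0.907 and a margin of 0.030-0.036; an assumed shift of 0.03 then leaves 0.80-0.82. Section 8.2, however, sizes the trial per stratum.

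**Primary exposure is partial.** Sections 5.1 and 8.1 define the primary endpoint through in vivo fluorescence intensity and PpIX concentration, and 8.1 puts the surgeon's score under the secondary objective. The effect on the primary comparison rests on Section 8.2, which is explicit that the score is what was sized.

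**Overlapping masses.** At an assumed 40-130 kg the masses run 400-1,300 and 800-2,600 mg and overlap from 800 to 1,300 mg, so the mass alone may not identify the arm. True, but a treating surgeon can be presumed to know the patient's weight.

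**Text not available.** The contents list a Section 7.2 (ALA Supply) between 7.1.2 and 7.3; its text was not available for review and could hold a safeguard. The wording of 7.1.2 would still conflict with 4.2.

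**Conclusion.** The concern holds. Section 7.1.2 permits, without requiring, an act that can defeat the blind in 4.2, and it does so for the person whose subjective score Section 8.2 uses to compare the doses. The conflict follows from the wording and needs none of the figures.

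The size and direction of any bias are unknown; it could help or harm selection of the better dose. What can be said is that, sized as in 8.2, a net shift toward the worse dose of at most 0.010 at ρ = 0.2, or at most 0.017 at ρ = 0.1, uses up the margin above 80%. This rests on the plan's own variances and sample counts, and on comparison within a stratum. The body weights and the shifts of 0.03 and 0.05 are assumptions. The point should be fixed: the inconsistency is real, it bears on the main comparison, and it is easily removed.

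**What to change.** Reconcile 7.1.2 with 4.2. In 7.1.2, keep the pharmacist and replace the surgeon or delegate with a second person who has no role in surgery, biopsy-site selection, fluorescence scoring or specimen reading, and who does not disclose the weight. Leave the emergency unblinding in 4.2 as it is.

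The change is one phrase. Weighing by two people is kept, and the sample size and analysis do not change. The cost is a small scheduling burden, because the second weigher must now come from outside the assessing team.
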